7.1.4 Other Efficacy Assessments

The study day (from Day 1 to Day 60 (± 3 days)) on which the following events occurred will be recorded:

- Initiation of supplemental oxygen (of any type)
- Discontinuation of supplemental oxygen (of any type)
- Initiation of respiratory support
- Discontinuation of respiratory support
- Initiation of antivirals or immune-modulating drugs
- Discontinuation of antivirals or immune-modulating drugs
- ICU admission
- ICU discharge
- Subsequent hospital admission for COVID-19 signs or symptoms
- Hospital discharge
- Death

Additionally, the following information will be gathered for each patient on Days 4, 8 (± 1 day), 15 (± 1 day), and 30 (± 2 days) (yes/no):

- Receiving supplementary oxygen therapy
- Receiving high-flow oxygen
- Receiving non-invasive mechanical ventilation
- Receiving invasive mechanical ventilation or ECMO
- Requiring hospital admission related to COVID-19
- Requiring ICU admission
- Receiving subsequent antiviral therapies or immunomodulatory
- Occurrence of new infection
- Death

Based on these data, secondary endpoints for percentages of patients requiring oxygen therapy or different types of ventilation will be calculated and the time (in days) to sustained hospital discharge or withdrawal of supplemental oxygen therapy, percentages of patients with new infection or receiving subsequent antiviral or immunomodulatory therapies, hospitalisation in ICU, and hospitalisation will be measured.

Laboratory based efficacy assessments that are to be performed during the study include:

- Proinflammatory biomarkers: (CRP, LDH, ferritin, cytokine multiplex Luminex[®] panel, including IL-1 β , IL-6, IL-10, and TNF α) in each study arm from baseline (Day 1 prior to start of the study treatment) to on Days 4 (± 1 day), 8 (± 1 day), 15 (± 1 day), 30 (± 2 days), and 60 (± 3 days),
- Anti-SARS-CoV-2 serologic and cellular response will be centrally assessed by validated tests, on Days 1, 30 (± 2 days), and 60 (± 3 days).

7.2 SAFETY AND TOLERABILITY ASSESSMENTS

Safety will be assessed throughout the study through clinical and laboratory safety evaluations. These include medical history at screening, physical examinations, vital sign measurements, saturation of oxygen (SpO₂) by pulse oximetry (or arterial blood gas analyses [PaO₂]), and its respective FiO₂ ([Appendix 7 - Imputation of FiO₂ from oxygen flow values. High-flow oxygen](#)

therapy), triplicate 12-lead ECGs, laboratory tests (haematology, coagulation, and chemistry), clinical AE monitoring, and verification of concomitant treatments.

Patients will be evaluable for safety if they have received any partial or complete treatment administration.

All adverse events (AE) and adverse reactions (ARs), based on clinical signs and symptoms and laboratory measurements, will be measured daily until Day 60 (± 3 days), except treatment-related adverse events, treatment-emergent adverse events of special interest, and SAEs that will be measured daily until resolution or stabilisation to at least Grade 1, or to an acceptable level according to the investigator and the Sponsor of his/her designated representative.

Adverse events will be elicited from the patient (or, when appropriate, from a caregiver, surrogate, or the patient's legally authorised representative) by the study site staff using a non-leading question such as "How are you feeling today?" or "Have you had any health concerns since your last visit?"

The investigator and any designees are responsible for detecting, documenting, and reporting events that meet the definition of an AE or SAE and remain responsible for following up AEs that are serious, considered related to the study treatment or the study, or that caused the patient to discontinue the study treatment (see [Section 7.4.2](#)).

Clinical Signs and Symptoms: AEs, including worsening of baseline signs and symptoms of disease observed by the investigator (preferably by the same physician for a same patient) or reported by patients to study nurses will be recorded and graded according to NCI-CTCAE version 5.0, accessible via internet (http://ctep.cancer.gov/protocolDevelopment/electronic_applications/docs/CTCAE_v5_Quick_Reference_8.5x11.pdf). All events, including those considered not related to the study drugs, must be reported in the eCRF.

Laboratory Abnormalities: Laboratory abnormalities will be recorded and graded according to NCI-CTCAE version 5.0, accessible via internet (http://ctep.cancer.gov/protocolDevelopment/electronic_applications/docs/CTCAE_v5_Quick_Reference_8.5x11.pdf). Laboratory abnormalities that are of clinical significance will be recorded in Adverse Event eCRF.

Laboratory abnormalities for which NCI CTCAE grading is not available will be classified as the fold below the lower limit of normal (<LLN) or fold above the ULN.

All AEs will be graded according to the NCI-CTCAE v.5. Treatment modifications and reason for treatment discontinuation will be monitored throughout the study. The latest MedDRA dictionary version will be used for AE coding.

The safety profile of patients will be monitored throughout the treatment and at Day 60 (± 3 days), or until the date of death, whichever occurs first.

Any treatment-related AEs, treatment-emergent adverse events of special interest, and SAEs will be measured daily until resolution or stabilisation to at least Grade 1, or to an acceptable level according to the investigator and the Sponsor of his/her designated representative.

7.2.1 Adverse Event of Special Interest

The following AEs will be considered and monitored as AEs of special interest (AESIs): musculoskeletal disorders, CPK increases, and rhabdomyolysis; hypersensitivity reactions, cardiac events and transaminase elevations, thromboembolic events, hepatobiliary disorders, and healthcare-associated infections (87).

If at any time AST/ALT levels are greater than 3 x ULN ($> 5 \times \text{ULN}$ if pre-existent liver involvement at baseline by the underlying disease, with baseline ALT levels between 3-5 x ULN):

- Report as an AESI.
- The investigator should ensure that serum liver enzyme tests, serum bilirubin, and coagulation tests (INR or equivalent) are repeated two or three times weekly (local labs). Frequency of re-testing can decrease to once a week or less if abnormalities stabilise or the trial drug has been discontinued and the subject is asymptomatic.
- The list of concomitant medications should be re-checked, and include nonprescription drugs, herbal and supplementary preparations, alcohol and recreational substances.
- Other reasons for liver injury should be ruled out, including co-infection with other virus, autoimmune or alcoholic hepatitis, non-alcoholic liver steato-hepatitis, biliary tract disease, progression of an underlying disease (e.g. liver metastasis), hypoxic/ischemic hepatopathy, or exposure to environmental agents.
- The investigator should consider additional tests to evaluate liver function or structure, as well as a consultation to specialists in liver diseases.

Treatment with pitidepsin must be discontinued in case of:

- ALT or AST $> 8 \times \text{ULN}$;
- ALT or AST $> 3 \times \text{ULN}$ and either total bilirubin $> 2 \times \text{ULN}$ or INR > 1.5 ;
- ALT or AST $> 3 \times \text{ULN}$ with the appearance of fatigue, nausea, vomiting, right upper quadrant pain or tenderness, fever, rash, and/or eosinophilia ($> 5\%$).

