4.1 INCLUSION CRITERIA

To be eligible for inclusion into this study, each patient must fulfil the following inclusion criteria within 48 hours prior to randomisation:

General inclusion criteria:

1. Signed informed consent obtained prior to initiation of any study-specific procedures and study treatment;
2. Patient aged ≥ 18 years;
3. Patient diagnosed COVID-19, with the following characteristics: a) A regulatory approved test, collected no more than 3 days prior to study randomisation, with either a Ct value ≤ 30 or a positive antigen test;
b) Presence of any of the selected signs/symptom listed in [Appendix 10 - COVID-19 signs/symptoms checklist](#) within the last 24 h;

4. Patient already admitted or requiring hospital care* for symptomatic COVID-19, for which at least one antiviral has failed[†] or cannot be used[‡], after a minimum washout period of 24h for small molecules (e.g., remdesivir, molnupiravir, nirmaltrevir/ritonavir) and 5 days for antiviral monoclonal antibodies (e.g., tixagevimab + cilgavimab) or convalescent plasma.

* The definition of hospital care is based on the need to use a hospital environment (hospital ward, day hospital) for treatment administration and/or clinical monitoring of the patient with COVID-19.

[†] Failure of a prior antiviral is defined as a documented lack of clinical response, plus evidence of persisting positivity for SARS-CoV-2 in an appropriate biological sample, determined by a regulatory approved test, collected no more than 3 days prior to study randomisation, with either a Ct value ≤ 30 (RT-PCR) or a positive antigen test.

[‡] Contraindication, absence of labelled indication, guidelines, or drug unavailability.

5. Adequate bone marrow, liver, kidney, and metabolic function, defined by the following tests performed at local laboratory:
 - Absolute neutrophil count $\geq 500/\text{mm}^3$ ($0.5 \times 10^9/\text{L}$);
 - Platelet count $\geq 50\,000/\text{mm}^3$ ($50 \times 10^9/\text{L}$);
 - Alanine transaminase (ALT) $\leq 3 \times$ upper limit of normal (ULN) ($\leq 5 \times$ ULN if pre-existent liver involvement by the underlying disease);
 - Serum bilirubin $\leq 1.5 \times$ ULN (or direct bilirubin $< 1.5 \times$ ULN when total bilirubin is above ULN);
 - Estimated glomerular filtration rate $\geq 30 \text{ mL/min}$ [CKD-EPI Creatinine Equation (2021)] (85).

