4.2 EXCLUSION CRITERIA

1. Evidence of critical illness, defined by at least one of the following:
 - Respiratory failure defined based on resource utilization requiring at least one of the following: endotracheal intubation and mechanical ventilation, ECMO, or clinical diagnosis of severe acute respiratory distress syndrome with $\text{PaO}_2^*/\text{FiO}_2 \leq 100$.
*In case a direct measure of PaO_2 has not been obtained, it should be imputed according to a referenced formula (Ellis or Rice) ([Appendix 5 - Imputation of \$\text{PaO}_2/\text{FiO}_2\$ ratio](#)). For sites located over 1000 m altitude above sea level, $\text{PaO}_2/\text{FiO}_2$ ratio will be adjusted ([Appendix 6- Adjustment of \$\text{PaO}_2\$ from a Site at High Altitude](#); See also [Appendix 7](#) for FiO_2 imputations from oxygen flow rates).
 - Shock requiring vasopressors.
 - Multi-organ dysfunction/failure.
2. (Criterion eliminated and merged with inclusion criterion #4 based on AEMPS recommendations).
3. Any of the following cardiac conditions or risk factors:
 - Cardiac infarction or cardiac surgery episode within the last month;
 - History of known congenital QT prolongation;
 - Known structural cardiomyopathy with abnormal LVEF (<50%);
 - Current clinical evidence of heart failure or acute cardiac ischaemia (New York Heart Association (NYHA) class III-IV).
4. Hypersensitivity to the active ingredient or any of the excipients (mannitol, macrogolglycerol hydroxystearate, and ethanol) or contraindication to receive dexamethasone, antihistamine H1/H2, or anti-serotonergic 5HT₃ agents.
5. Females who are pregnant or breast-feeding.
6. Females and males with partners of childbearing potential (females who are not surgically sterile or postmenopausal defined as amenorrhoea for >12 months) who are not using at least 1 protocol-specified method of contraception.
7. Any situation currently requiring increasing needs of immune suppressive agents (e.g. acute graft rejection, flare of autoimmune disorder, or cytokine storm syndrome).
8. Any other clinically significant medical condition (including major surgery within the last 3 weeks before screening) or laboratory abnormality that, in the opinion of the investigator, would jeopardise the safety of the patient or potentially impact on patient compliance or the safety/efficacy observations in the study.
9. Participation in another clinical study involving an investigational drug within 30 days prior to screening.

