5.7 EVALUATIONS AND PROCEDURES DURING TREATMENT

	ASSESSMENT/PROCEDURES	TIME
Clinical evaluation	
 COVID-19-related signs and symptoms checklist (Appendix 10 – COVID-19 signs/symptoms checklist). Clinical status (11-point WHO Clinical Progression Scale). Vital signs will include body temperature (°C), SBP (mmHg), DBP (mmHg), pulse rate (bpm) and respiratory rate (breaths/min). Targeted physical examination. A targeted physical examination will include heart, lungs, abdomen, extremities plus central nervous system (CNS) assessment, based on the investigator's decision as per clinical evolution. Lung function tests include PaO₂, FiO₂ and SpO₂. PaO₂/FiO₂ ratio will also be measured; either Ellis or Rice formulae can be used to estimate PaO₂/FiO₂ ratio (Appendix 5 - Imputation of PaO₂/FiO₂ ratio). 	Days 1, 2, 3, 4 (± 1). When applicable, these assessments should be performed before treatment administration.

	ASSESSMENT/PROCEDURES	TIME
	
 • Concomitant therapies. • Subsequent medications for SARS-CoV-2 infection. • Subsequent medications for the underlying disease. 	Days 1, 2, 3, 4.
Laboratory tests*	Haematology: haematocrit, red blood cells (RBC), differential WBC counts (including neutrophil and lymphocyte counts), platelet count and haemoglobin (See Appendix 8 – Clinical Laboratory Analyses).	Days 1, 4 (± 1), and whenever clinically indicated for an AE evaluation. When applicable, these assessments should be performed before treatment administration.
	Biochemistry: Liver function test [ALT, AP, AST [†] , albumin, total bilirubin (direct bilirubin if total is abnormally elevated)], lactate dehydrogenase (LDH), glucose [fasting], sodium, potassium, calcium, BUN/urea, gamma glutamyl transferase (GGT), creatinine, calculated creatine clearance [CKD-EPI], creatine phosphokinase (CPK), amylase, lipase, procalcitonin, ferritin, and CRP (See Appendix 8 – Clinical Laboratory Analyses).	Days 1, 4 (± 1), and whenever clinically indicated for an AE evaluation. When applicable, these assessments should be performed before treatment administration.
	Coagulation: D-Dimer (See Appendix 8 – Clinical Laboratory Analyses).	Day 1, 4 (± 1), and whenever clinically indicated for AE evaluation. When applicable, these assessments should be performed before treatment administration.
	Urine analysis (semi-quantitative elemental tests	Day 1 (previous to treatment administration). Repeat whenever

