11.7.1 Adverse Event of Special Interest

The following AEs will be considered and monitored as AEs of special interest (AESIs): musculoskeletal disorders, CPK increases, and rhabdomyolysis; hypersensitivity reactions, cardiac events and transaminase elevations, thromboembolic events, and hepatobiliary disorders.

If at any time AST/ALT levels are greater than 3 x ULN (> 5 x ULN if pre-existent liver involvement at baseline by the underlying disease, with baseline ALT levels between 3-5 x ULN):

- Report as an AESI.
- The investigator should ensure that serum liver enzyme tests, serum bilirubin, and coagulation tests (INR or equivalent) are repeated two or three times weekly (local labs). Frequency of re-

testing can decrease to once a week or less if abnormalities stabilise or the trial drug has been discontinued and the subject is asymptomatic.

- The list of concomitant medications should be re-checked, and include nonprescription drugs, herbal and supplementary preparations, alcohol and recreational substances.
- Other reasons for liver injury should be ruled out, including co-infection with other virus, autoimmune or alcoholic hepatitis, non-alcoholic liver steato-hepatitis, biliary tract disease, progression of an underlying disease (e.g. liver metastasis), hypoxic/ischemic hepatopathy, or exposure to environmental agents.
- The investigator should consider additional tests to evaluate liver function or structure, as well as a consultation to specialists in liver diseases.

Treatment with plitidepsin must be discontinued in case of:

- ALT or AST > 8 x ULN;
- ALT or AST > 3 x ULN and either total bilirubin >2 x ULN or INR >1.5;
- ALT or AST > 3xULN with the appearance of fatigue, nausea, vomiting, right upper quadrant pain or tenderness, fever, rash, and/or eosinophilia (>5%).

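### No scheduled liver result dependably precedes the third plitidepsin infusion, so the mandatory hepatic stop relies on clinically indicated tests; a rare eligible patient could also meet that stop before dose 1.

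*Protocol*

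**What the plan says.** **Stopping rule.** Protocol 7.2.1 states: "Treatment with pitidepsin must be discontinued in case of" any of three findings. The first is ALT or AST above 8 × ULN. The second, as SAP 11.7.1 gives it, is "ALT or AST > 3 x ULN and either total bilirubin >2 x ULN or INR >1.5". The third is ALT or AST above 3 × ULN with listed symptoms, rash or eosinophilia. None refers to the baseline value. The same section raises the threshold for reporting an event of special interest from 3 to 5 × ULN "if pre-existent liver involvement at baseline by the underlying disease, with baseline ALT levels between 3-5 x ULN", but that allowance covers only reporting and repeat testing.

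**Eligibility.** Inclusion 5 (Protocol 4.1) caps ALT at 3 × ULN, or 5 × ULN "if pre-existent liver involvement by the underlying disease". Total bilirubin must be at most 1.5 × ULN, or direct bilirubin must be below 1.5 × "ULN when total bilirubin is above ULN". AST is not limited, and the minimum screening panel in 5.5.1 does not list it. Exclusion 8 (4.2) allows exclusion for a "laboratory abnormality that, in the opinion of the investigator, would jeopardise the safety of the patient".

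**Schedule.** Infusions are on three consecutive days, every 24 h (±30 min) (6.1.4). Section 5.7 sets biochemistry on Days 1 and 4 (±1), "and whenever clinically indicated for an AE evaluation". A footnote sends all tests except screening to the central laboratory. The coagulation row reads "Coagulation: D-Dimer"; INR is not listed.

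**The concern.** A mandatory stop works only if the measurement reaches the site while there is still a dose to withhold. The plitidepsin course is over by Day 3, and the scheduled liver sample is centred on Day 4. A rise after the first or second dose could therefore go unseen until dosing is complete, unless symptoms or another event prompt a test.

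Separately, the limits for entry and for stopping were not reconciled. Where they overlap, a patient who passes inclusion 5 must be stopped although nothing has changed since screening. The site must then either breach the rule or keep the patient out by judgement.

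At stake are dosing decisions and the count of adverse events leading to treatment discontinuation, which SAP Table 3 still reports as frequencies in the As Treated population. The primary estimand follows patients regardless of treatment discontinuation and is not touched.

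**Working it through.** The plan gives no figure to reproduce here. The check sets the conditions and the calendar side by side.

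**Timing**

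1. Dosing days (6.1.4): 1, 2, 3.
2. Scheduled liver sample after dosing starts (5.7): Day 4 (±1), that is Days 3, 4 or 5. The Day 1 sample is taken before dosing.
3. Permitted days after dose 1 and before Day 3: none.
4. Permitted days after the day of the last infusion: Days 4 and 5, so 2 of 3.
5. The remaining day, Day 3, is the day of the third infusion. Section 5.7 would have the sample drawn before dosing, but it goes to the central laboratory, no turnaround is stated, and no text requires the result first.
6. Scheduled post-dose results that dependably precede infusion 3: 0.
7. The local repeat tests in 7.2.1, including INR, start only once ALT or AST is known to exceed the reporting threshold. For a patient with liver involvement and baseline ALT of 3–5 × ULN that threshold is 5 × ULN, although the bilirubin/INR limb applies from 3 × ULN. At two or three tests a week, a repeat need not fall before Day 3.

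**Eligibility against the stop** (values in multiples of ULN)

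| | Patient A, liver involvement | Patient B, no liver involvement |
|---|---|---|
| ALT | 4 | normal |
| AST | normal | 3.5 |
| Total bilirubin | 2.5 | 2.1 |
| Direct bilirubin | 1.2 | 1.0 |
| ALT criterion | 4 ≤ 5: met | normal ≤ 3: met |
| Bilirubin criterion | total > 1 and 1.2 < 1.5: met | total > 1 and 1.0 < 1.5: met |
| Bilirubin limb of the stop | 4 > 3 and 2.5 > 2: met | 3.5 > 3 and 2.1 > 2: met |

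Both patients satisfy inclusion 5 on their liver tests and meet a mandatory stop before dose 1. Patient A does not even reach the reporting threshold, since 4 is not above 5. The check before dosing in 5.5.1 asks only whether eligibility still holds, so it passes both. For Patient B, AST is first scheduled in the Day 1 central sample.

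The overlap comes from the direct-bilirubin route: if total bilirubin had to be at most 1.5 × ULN, the limb's requirement of more than 2 × ULN could not be met at entry.

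**The case against.** **On timing.** Section 7.2 says adverse events, including those based on laboratory measurements, are measured daily; 5.7 allows clinically indicated tests; and 7.2.1 provides local repeat testing. SAP 11.7 also refers to Appendix 8 to separate local from central tests, and Appendices 8 and 13 were not in the text reviewed. What stands is that the finding is provisional on those appendices and that some rises would be caught. But collecting events daily does not schedule a blood sample, and the other two routes need a prior trigger.

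**On eligibility.** The conflict needs a mainly unconjugated bilirubin rise together with a raised transaminase. Exclusion 8 could keep such a patient out, discontinuation can be read as referring to values on treatment, and where the rule bites it errs towards withholding drug. All of this stands and is why this part is minor. Exclusion 8 is still discretionary, and the rule does not say that it ignores baseline values.

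**Stronger readings to avoid.** A reader might take the 65.9% with new or worsening ALT in the earlier COVID-19 study (Protocol 1.2.1.3.1) as the share likely to hit a limit. The documents do not support that: the figure covers any new or worsening value, the events are described as reversible, mild and short-lasting, and no hepatocellular injury was reported. Nobody there had raised bilirubin at baseline, so it gives no size for the eligibility conflict either. Nor do the documents show that any patient was harmed, or that the stop could never operate.

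**Conclusion.** The concern holds in two parts of unequal weight.

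The main part is that, in the text reviewed, no scheduled post-dose ALT, AST or bilirubin result dependably reaches the site before the third infusion. In practice the mandatory stop depends on clinically indicated testing. This assumes that Appendices 8 and 13 add no earlier local sample. How many patients would cross 3 × or 8 × ULN before dose 3 cannot be derived from the documents.

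The minor part is that the wording lets a rare eligible patient meet the bilirubin limb before dose 1, either through ALT above 3 and up to 5 × ULN with liver involvement or through AST above 3 × ULN. The number is unknown and may be zero.

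A low-cost safety improvement is justified. The point does not cast doubt on the primary result. SAP 6.0 records early closure for low recruitment and a descriptive report, so the value lies in the plan as written and in any later protocol that reuses the rule.

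**What to change.** **Timing (main change).** In 5.7, for plitidepsin patients, add local ALT, AST and total bilirubin to the blood already drawn on Day 2 for cytokines, with INR if ALT or AST exceeds 3 × ULN. Require review against 7.2.1 before the Day 3 infusion. Fix this sample to Day 2 itself, because the synopsis gives the Day 2 biomarker time point a ±1 day window. Scheduled results before infusion 3 rise from 0 to 1.

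The cost is about 90 routine local panels at planned size (3 × 20 randomised + 30 in Group 4 = 90), with no extra venepuncture. The limitation is that the result reflects only one dose. A Day 3 sample would reflect two, but waiting for it risks breaching the ±30 min dosing window, from which only the first 30 pharmacokinetic patients are exempt, and SAP Table 2 counts incorrect timing as an important deviation.

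**Eligibility (minor change).** Add AST to the local screening panel in 5.5.1, and state in inclusion 5 that a patient with ALT or AST above 3 × ULN and total bilirubin above 2 × ULN is not eligible. The existing check before dosing then catches the conflict. The cost is one local test and a very small restriction of eligibility. INR is not in the minimum screening set, so the INR half of the limb stays unchecked at entry.

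Exempting patients with abnormal baseline values from the stop would also remove the conflict, but it loosens a mandatory hepatic safeguard and is not recommended.
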